1.1 Significance and Innovation

Intensive care units (ICUs) have one of the highest rates of healthcare-associated infections due the patients' severity of illness and frequent use of medical devices.^{1 2 3} We previously conducted a cluster-randomized trial of decolonization in adult ICUs (REDUCE MRSA Trial) in the Hospital Corporation of America (HCA) health system.⁴ We showed that ICUs using chlorhexidine (CHG) antiseptic for routine daily bathing and mupirocin antibiotic for nasal decolonization of all admissions experienced a 37% reduction in methicillin-resistant *Staphylococcus aureus* (MRSA) clinical cultures and a 44% reduction in all-cause bloodstream infection. Nasal mupirocin has been shown to be important because CHG does not clear the nasal reservoir of *S. aureus*, one of the most common and virulent healthcare-associated pathogens.^{5 6 7}

In response to the REDUCE MRSA Trial and other clinical trials,^{4 8 9} ICU decolonization has been adopted throughout HCA's ICUs and broadly across the United States. However, despite evidence showing that the combination of mupirocin and CHG is effective in reducing all-pathogen ICU infection as well as *S. aureus* carriage and infection,^{4 10 11 12} many hospitals outside HCA are omitting mupirocin due to concerns of eliciting mupirocin resistance. We found an increase in mupirocin resistance from 10% to 17% during the 18 month period of the REDUCE MRSA trial,¹³ and others have reported high rates of resistance in clinical settings.^{14 15 16 17 18 19}

Alternative agents that do not readily engender resistance to mupirocin but prevent infections are thus needed. This phenomenon of resistance emerging with use has been observed for many antibiotics. In contrast, antiseptics, such as alcohol, iodophor, and CHG, have not been shown to engender clinically meaningful resistance, likely due to their small molecular size.^{20 21 22 23 17 18 19 20 24} We did not identify CHG resistance in the REDUCE MRSA Trial,¹⁴ and prior studies evaluating antiseptics versus antibiotics for prevention of urinary tract infection or otitis media have found no evidence of antiseptic resistance.^{25 26} Of specific relevance to this study, iodophor resistance has not been reported despite over 50 years of use in healthcare and households.

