1.2.11 Outcomes

Individual level data from patients in all participating ICUs will be obtained from the HCA corporate data warehouse, including demographics, census (including ICU patient days), bathing queries, pharmacy (nasal decolonization product administration), diagnostic and procedure codes (enabling comorbidity score assessment), and microbiology testing results.

The primary outcome will be *S. aureus* clinical cultures (MRSA and MSSA) attributed to the participating ICU (>2 days into the ICU stay until 2 days after ICU discharge). Secondary outcomes intended for primary manuscript, include: 1) ICU-attributable MRSA clinical cultures, 2) ICU-attributable all-cause bloodstream infection.

Table 6. Mupirocin-Iodophor Swap Out Trial Outcomes

Outcome	Metric
Primary Trial Outcome	ICU-attributable S. aureus clinical cultures (MRSA + MSSA)
Secondary Trial Outcomes	ICU-attributable MRSA clinical cultures ICU-attributable all-cause bloodstream infection

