1.2.12 Data Collection

Descriptive data, outcome data and variables for addressing confounding will be derived from microbiology, census, pharmacy, and claims data from participating hospitals. The following data elements will be collected (Table 6) using encrypted study IDs.

Table 6. Data Elements

Source Data	Result Types	Elements
Microbiology: Finalized Results	All positive and negative cultures	Pathogen name (if culture is positive), patient identifier, date of collection, body site of collection, antimicrobial susceptibility
Census Data	Line item per admission	Patient identifier, hospital admission date, hospital discharge date, ICU vs. non-ICU charge code by calendar date, age in years, gender
Claims Data	Line item per admission	For case mix adjustment: Diagnosis codes (ICD9-ICD10) Procedure codes (ICD9/ICD10/CPT codes)
Pharmacy	Mupirocin and iodophor dispensing	Patient identifier, date range dispensed, ICU location

Nursing Queries	Bathing responses	Data on whether a bath was given, and if yes, with a CHG or non-CHG bathing soap product.
-----------------	-------------------	---

We will use claims data to collect diagnostic and procedure codes that will be used for case mix adjustment for both hospital-wide, ICU-specific, and post-ICU outcomes. Case mix will be assessed using a comorbidity score (e.g. Elixhauser score) as well as evaluating the individual components of that score (e.g. diabetes, renal disease) and evidence of major surgery.

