The primary outcome of the trial is ICU-attributable *S. aureus* clinical cultures (MRSA + MSSA) where ICU-attributable is defined as *S. aureus* cultures occurring in specimens collected from study cohort patients from the 3rd day of an ICU stay through 2 days after ICU discharge. This outcome will be assessed using an as-randomized unadjusted proportional hazards model as described above with two-sided significance set at alpha = 0.05, consistent with FDA standards of non-inferiority (<https://www.fda.gov/regulatory-information/search-fda-guidance-documents/non-inferiority-clinical-trials>). The pre-specified non-inferiority margin, we repeat, is 10%.

There is reason to suspect that nasal iodophor may be inferior to mupirocin due to FDA clearance based upon suppression versus cidal kill for *S. aureus*, which is the reason for the non-inferiority trial. However, conversely, if iodophor is found to be non-inferior, we are declaring the a priori intent to assess for superiority because of evidence of mupirocin-resistant *S. aureus* strains where none is expected to exist for iodophor. For this reason, if iodophor is found to be non-inferior in the primary outcome of the trial, we will also report the pre-specified assessment of superiority which is already performed in the primary analysis.

Secondary non-inferiority outcomes include 1) ICU-attributable MRSA clinical cultures and 2) ICU-attributable all-cause bloodstream infection. These will be assessed using an as-randomized unadjusted proportional hazards model as described above. We will use two-sided significance tests set at alpha = 0.05 for each outcome to determine possible inferiority with greatest possible sensitivity, again with a non-inferiority margin of 10%. Due to the above antibiotic-resistance rationale to suspect possible superiority, if non-inferiority is met for these secondary outcomes, we will perform a pre-specified assessment of superiority at a two-tailed significance set at alpha = 0.025, which accounts for the multiple comparisons of two outcomes. To be clear, the non-inferiority tests are not adjusted for multiple testing, while the superiority tests, if they are performed, will be adjusted for multiple testing, for conservatism.

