**Nasal Iodophor Antiseptic vs Nasal Mupirocin Antibiotic in the Setting of Chlorhexidine
Bathing to Prevent Infections in Adult ICUS: A Randomized Clinical Trial
NCT#: 03140423**

8/14/2019

Mupirocin-Iodophor Swap Out Trial

Statistical Analysis Plan

[name]
August 14, 2019

Background

Universal decolonization of all adult ICU patients with daily chlorhexidine (CHG) baths is widely implemented as ICU standard of care with and without nasal mupirocin due to several trials including the REDUCE MRSA Trial. This 43-hospital trial showed a relative 37% reduction in ICU-associated methicillin resistant *S. aureus* (MRSA) clinical cultures and a relative 44% reduction in all-cause bloodstream infections.

Combined use of CHG with mupirocin is driven by the fact that *Staphylococcus aureus* is a common community and healthcare-associated pathogen responsible for disease in ICU settings. Nevertheless, the variability in mupirocin resistance in various geographic areas (near zero to >15%) has led intensivists to be circumspect in whether they implement universal CHG bathing alone or with universal mupirocin. While the majority of MRSA are still susceptible to mupirocin, the concern about whether mupirocin resistance will continue to rise has led to interest in finding alternative effective agents.

For this reason, the Mupirocin-Iodophor Swap Out Trial was undertaken as a cluster randomized non-inferiority trial in 137 HCA Healthcare hospitals with hospitals randomized to:

Arm 1: Mupirocin-CHG (Usual Care)

Hospitals will continue daily bathing with chlorhexidine plus twice daily intranasal application of mupirocin ointment upon admission to all ICUs and continuing for 5 days or until discharge from the ICU.

Arm 2: Iodophor-CHG

Hospitals will continue daily bathing with chlorhexidine, but switch from mupirocin to twice daily intranasal application of 10% povidone-iodine (iodophor).

Trial Outcomes

Trial outcomes are found in the below table.

Mupirocin-Iodophor Swap Out Trial Outcomes

Outcome	Metric
Primary Trial Outcome	ICU-attributable S. aureus clinical cultures (MRSA + MSSA)
Secondary Trial Outcomes (primary manuscript)	ICU-attributable MRSA clinical cultures ICU-attributable all-cause bloodstream infection
Other pre-specified secondary exploratory analyses for later manuscripts	Mupirocin and iodophor resistance in MRSA isolates

Analysis

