The primary analysis will be an as-randomized proportional hazards model to evaluate for non-inferiority at a margin of 10% (difference in relative hazard). Model terms will include arm, period (baseline vs. intervention) and an arm by period interaction term to assess whether the difference in relative hazard between the baseline and intervention period differs significantly between the two arms. Clustering within hospital will be accounted for using shared frailties, i.e., a random intercept for each hospital, and, if it should become technologically feasible, an additional random intercept for each ICU within hospital and for repeated hospital stays for each person.

- Null hypothesis (H_0): the change in relative hazard of clinical culture of *S. aureus* in the Iodophor-CHG arm is higher than (inferior to) the change in the Mupirocin-CHG arm by more than 10%
- Alternative hypothesis (H_1): the change in relative hazard of clinical culture of *S. aureus* in the Iodophor-CHG arm is higher than (inferior to) the Mupirocin-CHG arm by 10% or less

Phase-in period data will not be included in the analysis.

To be explicit, the primary analysis will take the form of $\lambda_{ij}(t) = \lambda_0(t)e^{\beta_1 Arm_{ij} + \beta_2 Per_{ij} + \beta_3 Arm_{ij} * Per_{ij} + \gamma_i}$ where $\lambda_{ij}(t)$ is the time t of the *S. aureus* clinical culture for person j at hospital i . The baseline hazard function for time t , $\lambda_0(t)$, is shared by all people; γ_i is the frailty shared by patients at hospital i . The linear predictor in the exponent functions as in a linear model, where Arm_{ij} indicates the treatment arm of person j in hospital i is the iodophor arm, and Per_{ij} indicates that person j in hospital i was seen in the intervention period. Thus β_3 is the estimated differential effect of iodophor relative to mupirocin in the intervention period compared to baseline. While software is currently not able to include frailties for multiple visits per person or for multiple ICUs per hospital or for multiple periods per hospital on the scale of the data, we will include them if this should become possible by the time the trial is analyzed.

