The primary outcome of the trial is ICU-attributable *S. aureus* clinical cultures (MRSA + MSSA) where ICU-attributable is defined as *S. aureus* cultures occurring in specimens collected from study cohort patients from the 3rd day of an ICU stay through 2 days after ICU discharge. This outcome will be assessed using an as-randomized unadjusted proportional hazards model as described above with two-sided significance set at alpha = 0.05, consistent with FDA standards of non-inferiority (<https://www.fda.gov/regulatory-information/search-fda-guidance-documents/non-inferiority-clinical-trials>). The pre-specified non-inferiority margin, we repeat, is 10%.

There is reason to suspect that nasal iodophor may be inferior to mupirocin due to FDA clearance based upon suppression versus cidal kill for *S. aureus*, which is the reason for the non-inferiority trial. However, conversely, if iodophor is found to be non-inferior, we are declaring the a priori intent to assess for superiority because of evidence of mupirocin-resistant *S. aureus* strains where none is expected to exist for iodophor. For this reason, if iodophor is found to be non-inferior in the primary outcome of the trial, we will also report the pre-specified assessment of superiority which is already performed in the primary analysis.

Secondary non-inferiority outcomes include 1) ICU-attributable MRSA clinical cultures and 2) ICU-attributable all-cause bloodstream infection. These will be assessed using an as-randomized unadjusted proportional hazards model as described above. We will use two-sided significance tests set at $\alpha = 0.05$ for each outcome to determine possible inferiority with greatest possible sensitivity, again with a non-inferiority margin of 10%. Due to the above antibiotic-resistance rationale to suspect possible superiority, if non-inferiority is met for these secondary outcomes, we will perform a pre-specified assessment of superiority at a two-tailed significance set at $\alpha = 0.025$, which accounts for the multiple comparisons of two outcomes. To be clear, the non-inferiority tests are not adjusted for multiple testing, while the superiority tests, if they are performed, will be adjusted for multiple testing, for conservatism.

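### Does the primary endpoint need a rule for ICU stays that were already S. aureus-positive before ICU day 3?

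*SAP*

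**What the plan says.** The SAP (Analysis) counts as ICU-attributable those S. aureus "cultures occurring in specimens collected from study cohort patients from the 3rd day of an ICU stay through 2 days after ICU discharge". Protocol 1.2.13 has the same window, "from the 3rd day of an ICU stay through 2 days after ICU discharge". Protocol 1.2.11 expresses it as cultures "attributed to the participating ICU (>2 days into the ICU stay until 2 days after ICU discharge"), which comes to the same thing. The event is thus fixed by organism, cohort membership and specimen date.

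The exclusions in Protocol 1.2.1 and Table 1 apply to ICUs and hospitals: short mean length of stay, or a data system that cannot supply the records. None concerns a patient's earlier cultures. Protocol 1.2.12 collects all positive and negative cultures with collection dates, and "ICU vs. non-ICU charge code by calendar date", so a prior-positive stay could be identified if anyone wished to. The SAP's model is a proportional hazards model with arm, period, their interaction and a hospital frailty. It mentions an extra random intercept "for repeated hospital stays for each person" if software allows.

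Section 1.2.3 of the protocol was not in the text available to us, so a cohort definition there cannot be ruled out. The SAP contains none.

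**The concern.** A patient whose S. aureus culture was positive on the ward or on ICU day 1 may well have another positive culture on day 4. Under a strict idea of ICU-attributable infection, that second culture is old news. The documents do not mention the case, and the cohort from which specimens are drawn is not defined by culture history. Two datasets therefore seem possible: one that keeps such stays and one that drops them.

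Two consequences would follow. First, the claim turns on a hazard-ratio margin of 1.10 at about 82% power, so removing part of the events can move the confidence limit across the margin. Second, any later positives that the nasal product cannot influence pull the hazard ratio towards 1. In a non-inferiority trial that favours success. The MRSA and bloodstream outcomes use the same window and share the question.

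**Working it through.** **Inputs from the documents.** Margin 1.10 and two-sided alpha 0.05 (SAP, Analysis). Power 82% with 120 hospitals, iodophor assumed to eradicate 5% more, 4.8 cases per 1,000 ICU-days and about 171,500 patients (SAP, Power and Sample Size). The SAP's Background describes a "cluster randomized non-inferiority trial in 137 HCA Healthcare hospitals".

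**Assumptions.** The 5% is read as a true hazard ratio (HR) of 0.95. The share p of counted events that fall in prior-positive stays is not given, so a range is used, equal across arms and periods. The planned 82% is taken as including these events. Unless stated otherwise, variance scales with the number of events.

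**Step 1: standard error implied by the plan.** The 82% came from a simulation whose days at risk and frailty variance are not reported, so it can be neither confirmed nor refuted. It is used as an anchor:

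SE = (ln 1.10 − ln 0.95) / (1.960 + 0.915) = 0.1466 / 2.875 = 0.0510.

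For 137 hospitals: 0.0510 × √(120/137) = 0.0477.

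**Step 2: opposite verdicts when the two sets of events have the same HR.** Keeping all events gives SE 0.0510. Dropping a share p gives SE 0.0510/√(1−p). The correlation of the two estimates is √(1−p). Power is Φ(ln(1.10/0.95)/SE − 1.960). At p = 20%:

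- keep: Φ(0.915) = 82.0%
- drop: SE 0.0570, Φ(0.612) = 73.0%
- both succeed (bivariate normal): 70.9%
- keep succeeds, drop fails: 82.0 − 70.9 = 11.1%
- drop succeeds, keep fails: 73.0 − 70.9 = 2.1%
- opposite verdicts: 13.2%

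| p | Power, keep | Power, drop | Opposite verdicts, 120 hospitals | of which keep succeeds, drop fails | Opposite verdicts, 137 hospitals |
|---|---|---|---|---|---|
| 5% | 82.0% | 80.0% | 5.1% | 3.5 points | 4.3% |
| 10% | 82.0% | 77.9% | 7.9% | 6.0 points | 6.7% |
| 20% | 82.0% | 73.0% | 13.2% | 11.1 points | 11.5% |
| 30% | 82.0% | 67.2% | 19.0% | 16.9 points | 17.1% |

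Nothing in this calculation is specific to prior-positive stays. Dropping any random 20% of events gives the same 13.2%.

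**Step 3: the variance assumption.** If part of the variance lies between hospital-periods, both rules share it and it does not grow when events are dropped. With the total SE held at 0.0510, and 4, 5 or 7 days at risk per patient (assumed), the 13.2% falls to 11.5%, 10.0% or 8.1%.

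**Step 4: dilution.** Suppose half of the prior-positive events are independent of product, and the HR in all other events is exactly 1.10. The HR over all counted events is then p/2 + (1 − p/2) × 1.10.

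| p | HR over all counted events | Chance of declaring non-inferiority |
|---|---|---|
| 5% | 1.0975 | 2.8% |
| 10% | 1.095 | 3.1% |
| 20% | 1.09 | 3.7% |
| 30% | 1.085 | 4.5% |

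The reference is 2.5%. For the endpoint as the SAP defines it, however, the HR in every row is below 1.10. Non-inferiority is then true, and declaring it is not an error.

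**Step 5: what the text yields as written.** The window has no condition on earlier cultures, and no listed exclusion removes a patient for one. To drop prior-positive stays an analyst must add a criterion that appears nowhere in the text available to us. Read literally, the plan gives one dataset: a positive specimen inside the window counts.

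**The case for a change.** The best argument for a change is that the plan nowhere confirms the literal reading. The label ICU-attributable suggests incident events, the cohort is undefined, and neither the as-treated nor the adjusted analysis would show how much the choice matters. The SAP was updated before the dataset was accessed, so a sentence could have been added without data influence. The dates needed are already collected.

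The silence is real, and stating the rule would cost almost nothing. The consequence is not shown, for three reasons.

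- The documents themselves say what ICU-attributable means: a specimen window. An incident-only reading replaces that definition with another.
- Keeping prior-positive stays is scientifically reasonable. Protocol 1.1 justifies a nasal agent because "CHG does not clear the nasal reservoir", so later cultures in patients who already carry the organism may be among those that the product affects.
- Dropping stays positive on ICU days 1–2 has its own defect. The SAP describes "intranasal application of mupirocin ointment upon admission to all ICUs", so those cultures are taken after treatment starts, and the filter would condition on post-treatment data. Dropping would also cost power: 9.0 points at p = 20% if prior-positive events respond to product like the rest (82.0 − 73.0). If none of them responds, keeping gives an HR of 0.96 and power of 76.1%, and dropping still costs 3.1 points.

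A descriptive analysis without stays positive before ICU entry would be a harmless addition. It would not decide the claim.

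**Conclusion.** The concern identifies a missing sentence, not a defect. Followed as written, the plan counts every S. aureus-positive clinical specimen in the window, identically by arm and period, and the as-randomized comparison is sound. The arm-by-period contrast, and a randomization that aims to balance baseline outcome values (Protocol 1.2.5), further limit any differential effect. No stated figure or rule is shown to be wrong.

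The opposite-verdict range of 5.1% to 19.0% rests on an assumed p of 5% to 30%, a back-solved standard error and an HR of 0.95. It arises only if someone applies a filter that the plan does not contain, and at each p most of it is power lost by discarding events. The dilution figures of 2.8% to 4.5% are not an inflated error rate for the endpoint as defined.

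This is a gap that analysts can fill sensibly by taking the definition at its word. Confirming the literal rule and defining the cohort would be good housekeeping, here and for the MRSA and bloodstream outcomes. No change to the analysis follows.

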Additional analyses will include as-treated and adjusted models, which will be reported as point estimates with confidence intervals without p-values. The reason for including these analyses is to provide additional information related to the trial outcomes for reader assessment of potential confounders. The reason to not include them in a formal multiple comparisons adjustment is because these analyses are non-independent evaluations related to the as-randomized unadjusted analyses.

Power and Sample Size

While 140 HCA hospitals are eligible for recruitment, we have HCA corporate commitment to assure the participation of at least 120 hospitals. Power was assessed using simulation methods. We simulated hospitals using information from HCA regarding ICU size and from a prior trial (REDUCE MRSA Trial) regarding likely rates of *S. aureus* in the baseline period. With 120 hospitals, we will have 82% power to detect non-inferiority within a hazard ratio of 1.1, based upon 2014 HCA ICU-attributable *S. aureus* clinical cultures of 4.8 cases per 1,000 ICU-days. While the intent is to confirm non-inferiority, we assume that iodophor will eradicate 5% more *S. aureus* than mupirocin due to existing mupirocin resistance. We estimate that total ICU patients in the intervention period will be ~171,500 patients who stay >2 ICU days.

NOTE: This statistical analytic plan was updated post-completion of the trial, but prior to accessing the trial dataset for cleaning or analysis. It was updated in response to the Harrington et al. (NEJM 2019;381:285-6) publication on “New Guidelines for Statistical Reporting in the *Journal*.”

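### Does the 82% power figure overstate the trial's ability to show non-inferiority because it assumes iodophor is 5% better than mupirocin?

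*SAP*

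**What the plan says.** The SAP, under Power and Sample Size, gives one power figure: "With 120 hospitals, we will have 82% power to detect non-inferiority within a hazard ratio of 1.1". It comes from simulation and rests on "clinical cultures of 4.8 cases per 1,000 ICU-days". The next sentence reads "While the intent is to confirm non-inferiority, we assume that iodophor will eradicate 5% more" *S. aureus* than mupirocin, because of existing mupirocin resistance. The paragraph closes with the expected volume: "We estimate that total ICU patients in the intervention period will be ~171,500 patients who stay >2 ICU days". Protocol 1.2.13 has the same text.

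The SAP Analysis section tests the arm-by-period interaction against a 10% margin, "with two-sided significance set at alpha = 0.05, consistent with FDA standards of non-inferiority". It explains the choice of design with "There is reason to suspect that nasal iodophor may be inferior to mupirocin". It then says that superiority is also possible, because mupirocin-resistant strains exist and none are expected for iodophor.

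The power paragraph treats 120 hospitals as the assured minimum. The SAP Background says that "the Mupirocin-Iodophor Swap Out Trial was undertaken as a cluster randomized non-inferiority trial in 137 HCA Healthcare hospitals".

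**The concern.** A reader who sees 82% beside a margin of 1.1 may take it as the chance of success if the two products work equally well. The 5% assumption makes it the chance of success if iodophor is somewhat better. Moving the true effect from slightly better to equal uses up a large share of the distance to a 10% margin, so power should fall sharply. The plan also says it fears iodophor may be worse, yet gives no power at equality or on the unfavourable side. The paragraph still uses 120 hospitals although 137 took part.

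The risk is in interpretation. If the chance of success at equality is near one half, a failed test says little about whether iodophor is worse. A reader who relies on 82% might think it says a good deal.

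**Working it through.** **Inputs.** From the documents: 82% power, 120 hospitals, margin 1.10, two-sided alpha 0.05 (z = 1.960), 4.8 events per 1,000 ICU-days, 171,500 intervention-period patients, 24 months of baseline, 18 months of intervention and 137 hospitals taking part. Assumed: 5% more eradication means a true hazard ratio (HR) of 0.95. The documents state no HR for it.

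**Step 1: the plan's own figure.** The 82% cannot be rebuilt exactly, because neither ICU-days per patient (d) nor between-hospital variance is reported. An approximate forward check uses:

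- intervention events E1 = 171,500 × d × 0.0048, and baseline events E0 = E1 × 24/18;
- Var(log HR) = 1/(E1/2) + 1/(0.95 × E1/2) + 2/(E0/2);
- power = Φ[(ln 1.10 − ln 0.95)/SE − 1.960].

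Results at HR 0.95 with no extra cluster variance: 61% at d = 2, 78% at d = 3, 81% at d = 3.27 and 94% at d = 5. With d = 5, a hospital-by-period SD of about 0.11 brings power back to 82%. So 82% at HR 0.95 is attainable on plausible inputs. For 82% at HR 1.00, the same approximation needs d of about 7.7 (some 6,370 intervention events) and almost no extra variance. This favours the HR 0.95 reading but does not prove it.

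**Step 2: standard error implied by 82% at HR 0.95.**

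SE = (ln 1.10 − ln 0.95)/(1.960 + 0.915) = (0.0953 + 0.0513)/2.875 = 0.0510.

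**Step 3: power at other true HRs, 120 hospitals.** Power = Φ[(0.0953 − ln HR)/0.0510 − 1.960].

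| True HR | Power |
|---|---|
| 0.95 | 82% |
| 0.975 | 66% |
| 1.00 | 46% |
| 1.025 | 28% |
| 1.05 | 15% |

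The largest estimate that passes is exp(0.0953 − 1.960 × 0.0510) = 0.995.

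**Step 4: 137 hospitals.** If the SE scales with the number of hospitals, it is 0.0510 × √(120/137) = 0.0477. Power is then 87% at HR 0.95 and 51% at HR 1.00. The largest passing estimate is exp(0.0953 − 1.960 × 0.0477) = 1.002.

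**Step 5: other readings of the 5%.** Two of them take the 37% reduction quoted from the earlier decolonization trial as an illustrative level of eradication. A relative 5% gain gives (1 − 0.37 × 1.05)/(1 − 0.37) = 0.971. A gain of five percentage points gives (1 − 0.42)/(1 − 0.37) ≈ 0.92.

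| 82% taken to hold at | Implied SE | Power at HR 1.00, 120 hospitals | 137 hospitals |
|---|---|---|---|
| HR 0.95 | 0.0510 | 46.4% | 51.5% |
| HR 1/1.05 | 0.0501 | 47.7% | 52.9% |
| HR 0.971 | 0.0435 | 59.1% | 64.8% |
| HR 0.92 | 0.0622 | 33.5% | 37.4% |
| HR 0.95, one-sided 0.05 | 0.0573 | 50.8% | 55.3% |

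**Step 6: what 82% at equality would take.** The information needed rises by (0.1466/0.0953)² = 2.37. If information scales with hospitals, that is 120 × 2.37 ≈ 284 hospitals, against the 140 the plan calls eligible.

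**The case for a change.** The strongest case for changing the plan runs as follows. Every reading in step 5 leaves power at equality well below 82%. Disclosing an assumption does not tell the reader how steeply power drops when it fails. The SAP was revised before the dataset was accessed, so one more simulation run and an updated hospital count would have cost little. The SAP also describes the secondary tests as looking for possible inferiority, which could encourage someone to read a failed test as harm.

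Much of this stands as description. Power at equality is not given, it is much lower than 82%, and an extra line would have informed readers. The step from there to a defect does not stand:

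- **The figure is not misstated.** The assumption is in the sentence after the 82%, and nothing shows the design falls short under it.
- **The assumption has a stated basis.** The SAP's worry about inferiority is followed by its argument for possible superiority. Protocol 1.1 reports mupirocin resistance rising from 10% to 17% during the earlier trial.
- **The stronger consequences fail for the trial as run.** With 137 hospitals on the HR 0.95 reading, a miss at equality is not more likely than success (51% power), and iodophor need not look numerically better (largest passing estimate 1.002).
- **Quoting 120 hospitals is conservative.** It is the assured minimum; on the same scaling, 137 raises 82% to 87%.
- **The hypotheses already govern interpretation.** Under the SAP's null and alternative, an upper limit at or above 1.10 means the null is not rejected, so non-inferiority has not been shown. That is not a finding of inferiority.

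**Conclusion.** No change follows. Planning on a modest true benefit is a disclosed trade-off: on the HR 0.95 reading, holding 82% power at equality would take about 284 hospitals where 140 were eligible.

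Power at equality is about 46% with 120 hospitals and about 51% with 137. These figures are conditional. They assume that the 82% was simulated at HR 0.95 with two-sided 0.05 and, for 137, that the added hospitals resemble the rest. Other readings of the 5% span about 33% to 59% with 120 hospitals and about 37% to 65% with 137.

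What is missing is a sensitivity figure. It would have been most useful when the trial was being sized. By the SAP's date the trial was complete, and the precision achieved will show directly in the confidence interval for the interaction. A revised power statement would not alter the estimand, the margin, the test or any conclusion the data can support. Reporting power at HR 1.00, with the simulation inputs, remains an optional courtesy to readers.
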